APPENDIX C. RETESTING SCHEMA FOR SUBJECTS WITH CHANGES IN KIDNEY FUNCTION

Abbreviations: BL, Baseline; eCrCl, estimated creatinine clearance; IP, investigational product; sCr, serum creatinine.

RETEST 1, RETEST 2, and RETEST 3 are performed approximately 1 to 2 weeks, 2 to 4 weeks, and 7 to 8 weeks relative to the test result that first met the criteria.

^a If the criteria for IP interruption have been met on 3 separate episodes during the course of the study, IP needs to be permanently discontinued.

^b For all assessments after the Month 12 study visit, the criterion for retesting changes to “eCrCl >40% decline from BL”.

^c For all assessments after the Month 12 study visit, the criterion for resolution changes to “eCrCl ≤20% decline from BL”.

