5.3.2.1. Investigational Product and Xanthine Oxidase Inhibitors

IP (lesinurad or placebo) is only permitted at 200 mg qd. No dose reductions or dose escalations of IP are permitted. The prescribed dose and dosing regimen of XOI should also be continued unchanged throughout the study, unless adjusted for toxicity. Study treatment (IP or XOI) may be interrupted due to AEs or for suspected toxicity.

If XOI is interrupted for any reason, **IP must be interrupted concurrently**. When medically appropriate, the XOI should be resumed, at which time IP may also be resumed. The XOI may be resumed at the same dose; lower doses (if available) are only permitted if the XOI had been interrupted due to a TEAE considered related to that XOI. If resumed at a lower dose, the XOI should be increased up to the original dose, as tolerated. Subjects should not be maintained on a dose of allopurinol <200 mg daily.

If IP is interrupted for any reason, the subject is permitted to continue XOI, as tolerated. When medically appropriate, IP should be resumed, but must only be resumed if the subject is taking XOI.

5.3.2.1.1. Interruption or Discontinuation of Investigational Product Due to Changes in Kidney Function

Kidney function will be monitored throughout the study by measuring sCr and calculating eCrCl by Cockcroft-Gault formula using ideal body weight. All clinically meaningful changes in kidney function should be evaluated and managed as medically appropriate, including interrupting IP and study medications if needed.

IP must be **temporarily interrupted** if a subject experiences an absolute sCr ≥ 4.0 mg/dL or an eCrCl <20 mL/min (based on central laboratory results), and the subject will be required to return to the site for retesting (see [Section 6.12](#)). IP may be resumed at the Investigator's discretion if eCrCl is within 15% of Baseline if this occurs through the Month 12 study visit, or if eCrCl is within 20% of Baseline if this occurs from the Month 12 study visit through the Month 24 study visit.

IP should be **permanently discontinued** if there are more than 3 episodes of interruption of IP due to any of the following:

- If the Investigator or Healthcare Provider temporarily interrupts IP due to changes in kidney function,
- If the Investigator or Healthcare Provider temporarily interrupts IP due to any safety concerns due to IP, or
- Protocol-specified criteria for interruption are met (ie, sCR ≥ 4.0 mg/dL or eCrCl <20 mL/min).

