An episode is defined as the interruption and then re-initiation of IP, regardless of the duration of the interruption. The fourth interruption should be considered permanent when based on the above criteria.

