5.3.2.1.2. Other Reasons, and Procedures, for Permanent Discontinuation of Investigational Product

As much as possible and permitted by the protocol, subjects should be encouraged to continue on IP for the full 24-month Treatment Period.

Subjects have the right to permanently discontinue IP at any time for any reason. Investigators may also discontinue IP if they determine that it is not in the best interest of the subject to continue. All subjects should be encouraged to remain in the study even if IP has been discontinued for any reason.

IP must be permanently discontinued if the subject meets any of the following criteria:

- Subject permanently discontinues XOI.
- Subject becomes pregnant.
- Subject initiates chronic therapy with any of the following medications:
 - valpromide, progabide, valproic acid, or other known inhibitors of epoxide hydrolase.
 - any approved ULT indicated for the treatment of gout (eg, benzbromarone, probenecid, pegloticase, commercially-available lesinurad), except those required per protocol (allopurinol and febuxostat).
 - azathioprine or mercaptopurine.
- Subject requires dialysis or kidney transplantation.
- Subject has temporarily interrupted IP for more than 3 separate episodes at any time on study due to changes in kidney function, based on any safety concern due to IP by the Investigator or Healthcare Provider, or where protocol-specified criteria for interruption have been met (ie, sCr \geq 4.0 mg/dL or an eCrCl $<$ 20 mL/min).

The date and the reason must be recorded on the appropriate Case Report Form (CRF) for all subjects who discontinue IP. If the reason is an AE, the specific AE must be identified on the CRF.

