6.12. Retest Requirements for Subjects With Changes in Kidney Function

Retesting of laboratory values, including sCr and eCrCl, as well as the interruption of IP due to safety concerns, can occur any time on study at the Investigator's discretion.

If a subject experiences any of the following changes in kidney function (using central laboratory results), the subject must return to the site for retesting and be evaluated for potential contributing factors:

- eCrCl declines >30% from Baseline in the period starting at Baseline through Month 12 study visit, or eCrCl declines >40% from Baseline in the period from the Month 12 study visit through the Month 24 study visit.
- Absolute sCr \geq 4.0 mg/dL or eCrCl <20 mL/min at any time on study (Note: this is also the criteria for when IP must be interrupted; see Section 6.12.1.)

The underlying cause of the change in kidney function should be evaluated, treated, and managed as medically appropriate by the Investigator. Additional information will be collected on these events in the CRFs.

During any Retest periods throughout the study period, IP does not need to be interrupted unless warranted as determined by the Investigator and treating Healthcare Providers or if specific criteria are met (sCr \geq 4.0 mg/dL or an eCrCl < 20 mL/min; see Section 6.12.2).

For IP discontinuation criteria see Section 5.3.2.1.2. Retesting schema for subjects with changes in kidney function is presented in Appendix C.

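### Appendix C makes IP discontinuation permanent at 3 interruption episodes; Sections 5.3.2.1.1 and 5.3.2.1.2 do so only beyond 3

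*Combined protocol and SAP*

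**What the plan says.** Four places in the current Version 3 protocol bear on this; none is amendment-log text.

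- **Appendix C, footnote a**, reads: "If the criteria for IP interruption have been met on 3 separate episodes during the course of the study, IP needs to be permanently discontinued".
- **Section 5.3.2.1.1:** IP should be permanently discontinued "if there are more than 3 episodes of interruption of IP due to any of the following". Three types of interruption follow: those made for changes in kidney function; those covered by "If the Investigator or Healthcare Provider temporarily interrupts IP due to any safety concerns due to IP"; and those where the protocol's laboratory criteria are met (sCr ≥4.0 mg/dL or eCrCl <20 mL/min). An episode is an interruption followed by re-initiation, of any duration. The section closes: "The fourth interruption should be considered permanent when based on the above criteria".
- **Section 5.3.2.1.2**, in its list of mandatory reasons for stopping: "Subject has temporarily interrupted IP for more than 3 separate episodes at any time on study". The laboratory criteria are again included.
- **Section 6.12**, in consecutive sentences: "For IP discontinuation criteria see Section 5.3.2.1.2" and "Retesting schema for subjects with changes in kidney function is presented in Appendix C".

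On restarting, Section 5.3.2.1.1 allows IP to resume at the Investigator's discretion "if eCrCl is within 15% of Baseline if this occurs through the Month 12 study visit", with 20% in place of 15% after that. Section 6.12.2 adds that sCr must be below 4.0 mg/dL and eCrCl at least 20 mL/min.

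**The concern.** Three and more than three are different thresholds, and the protocol does not say which prevails. A site handling a renal event from the retesting schema reads footnote a, which is a complete instruction by itself. A site working from Section 5.3.2.1.2 reads the other count. With up to about 300 sites, subjects with the same history could be handled differently.

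The consequences reach beyond conduct:

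- Sections 3.2.1 and 9.4.2.2 list the incidence of subjects meeting treatment-discontinuation criteria as a safety outcome. With two thresholds, a subject with exactly three laboratory-triggered episodes can be counted or not.
- Section 6.11.1 requires protocol-mandated permanent discontinuation under the sCr/eCrCl criteria to be reported as an AE. Under Section 6.11.1.1, renal events leading to permanent discontinuation are AEs of special interest.
- Section 9.4.2.1 sets renal function values after IP discontinuation to missing before the main MMRM, so the rule a site follows can decide which eCrCl values enter that analysis.

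**Working it through.** The plan gives no figure to reproduce. The check is a comparison of the rules at one count, followed by arithmetic on how far eCrCl must move for an episode to occur and resolve.

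**Step 1: apply each rule at the third episode.** Take a subject who has met sCr ≥4.0 mg/dL or eCrCl <20 mL/min on exactly 3 occasions, has no other interruptions, and has now recovered enough to qualify for restart.

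| Source | Condition for permanent discontinuation | Met at count 3? | Result |
|---|---|---|---|
| Appendix C, footnote a | 3 episodes | Yes | Must stop |
| Section 5.3.2.1.1 | More than 3; fourth interruption permanent | No | May restart |
| Section 5.3.2.1.2 | More than 3 | No | May restart |

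**Step 2: check whether scope removes the conflict.** The body text also counts interruptions made by the Investigator or Healthcare Provider, whereas footnote a refers only to the criteria for interruption. Both body sections nevertheless apply the higher count to the laboratory criteria, so the conflict remains for a subject with laboratory-triggered episodes only.

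**Step 3: size of the swing behind each episode (eCrCl trigger only).** Inputs: trigger eCrCl <20 mL/min; restart within 15% of Baseline through Month 12 and within 20% afterwards (Sections 5.3.2.1.1 and 6.12.2).

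- Fall needed: more than 1 − 20/Baseline
- Restart level: 0.85 × Baseline through Month 12; 0.80 × Baseline afterwards

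| Baseline eCrCl (mL/min) | Fall needed | Restart level through Month 12 | Restart level after Month 12 |
|---|---|---|---|
| 30 | >33.3% | 25.5 | 24.0 |
| 40 | >50.0% | 34.0 | 32.0 |
| 45 | >55.6% | 38.25 | 36.0 |
| 59.9 | >66.6% | 50.9 | 47.9 |

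For Baseline 30: 1 − 20/30 = 33.3%; 0.85 × 30 = 25.5; 0.80 × 30 = 24.0.

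These rows are illustrative. The 30.0 to <60.0 mL/min limits apply to Screening eCrCl, the average of two screening visits. Baseline is a separate, later measurement for which no eCrCl limit is stated, and a single screening value may be as low as 25.0 (Section 4.2). At an assumed Baseline of 25, the fall needed is more than 1 − 20/25 = 20%, and the restart levels are 0.85 × 25 = 21.25 and 0.80 × 25 = 20.0.

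The swing is thus smallest for subjects entering at the low end. The 30.0 to <45.0 mL/min stratum is planned as about half of some 600 subjects (Sections 9.1 and 9.2), or 0.5 × 600 = 300. The sCr trigger is not modelled because the corresponding eCrCl depends on age, sex and height.

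**The case against.** The strongest reply is that the texts can be read together and little turns on the difference.

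- **Episode definition.** An episode ends only on re-initiation, so three episodes could mean three completed cycles, with the next interruption, the fourth, permanent. This does not work for footnote a, which counts the interruption criteria having been met and does not mention re-initiation.
- **Cross-references.** Section 6.12 points to Section 5.3.2.1.2 for discontinuation criteria, and Section 6.11.1 points to Section 5.3.2.1.1. That makes the body text the likelier source for a careful reader. It is still not a precedence rule, and footnote a remains an instruction in force.
- **Discretion.** Restart is optional and an Investigator may stop IP at any time, so stopping at the third episode need not breach the body text. That is correct, but restarting after the third episode would breach Appendix C while being allowed by the body text.
- **Limited effect on the analysis.** The set-to-missing rule works from the actual discontinuation, whose date is recorded on the CRF, so it is defined whichever count a site follows. A planned sensitivity analysis also keeps off-IP data. Both points stand and limit the effect on the MMRM.
- **Rarity.** Three episodes with recovery and restart in one subject are probably uncommon. This stands as a judgement; the protocol offers no rate to test it.

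The Appendix C figure is not available here, so the footnote's anchor cannot be seen. Its wording is complete, and nothing above depends on the figure.

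**Conclusion.** The contradiction is real. At exactly three laboratory-triggered episodes with recovery, Appendix C requires permanent discontinuation, while Sections 5.3.2.1.1 and 5.3.2.1.2 permit restart. No reading of the current text makes them agree.

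The number of subjects affected cannot be estimated from the protocol. The expectation that it is small is a judgement; the swing arithmetic only shows that an episode is easiest to reach at low Baseline eCrCl. The case for correction does not rest on bias in the MMRM. It rests on a mandatory stopping rule with two values in a trial whose primary objective is safety with a renal focus, and on an endpoint defined by meeting such criteria. It must be fixed. Which count is right is a clinical decision and is not judged here.

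**What to change.** Reconcile Appendix C, footnote a, with Sections 5.3.2.1.1 and 5.3.2.1.2 so that one count applies everywhere, and describe the types of interruption that count in the same words in each place. The sponsor's clinical team decides the rule.

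In the same edit, align the Retest 2 window, which is 2 to 4 weeks in Appendix C and 3 to 4 weeks in Sections 6.12.1 and 6.12.2. This is a minor point.

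The cost is one footnote or sentence plus the retest window in a protocol amendment. Sample size, data collection and planned analyses do not change.

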1. RATIONALE FOR AMENDMENT

The primary purpose of this amendment is to address regulatory feedback and to add a Month 1 study visit. Per the original protocol, the first on-treatment visit was scheduled for Month 3.

In addition, minor revisions to improve clarity or provide additional detail have been made to language describing study entry criteria; pregnancy and fertility testing; sourcing, dispensing, and dosing of study medications; premature discontinuation from the study; analysis populations; definition of adverse events (AEs); AEs of special interest; gout flare assessments; and current cumulative lesinurad exposure data.

Finally, minor editorial changes have been made to improve readability; these changes will not be discussed in this document.

2. SUMMARY OF CHANGES

2.1. Addition of a Site Visit at Month 1 (Day 28 ± 7 Days)

The Month 1 visit will include all of the same assessments and procedures as the Month 3 visit, except for patient-report outcomes (PROs) and dispensing of study medication. In addition to data collection, it will be an earlier opportunity for subject education regarding the importance of study medication compliance, particularly taking investigational product (IP; lesinurad or placebo) in combination with their xanthine oxidase inhibitor (XOI).

This additional visit is reflected in the following sections of the protocol:

- [Synopsis \(Methodology section\)](#)

- [Section 3.1. Overall Study Design and Plan](#)
- [Section 8.3.2. Month 1 \(Day 28 ±7 days\) and Months 3 Through 21 \(Visits Every 3 Months ±7 days\)](#)
- [Appendix A Schedule of Events.](#)

2.2. Inclusion and Exclusion Criteria

The language regarding ineligibility of women who are pregnant or breastfeeding has been strengthened (appearing now under both Inclusion Criteria and Exclusion Criteria), an exclusion criterion for subjects with a history of glomerulonephritis has been added, and the exclusion criterion regarding concomitant use of CYP3A inhibitors has been revised to specify that it applies to subjects who will be taking colchicine for gout flare prophylaxis.

These changes are reflected in the following sections of the protocol:

- [Synopsis \(Eligibility Criteria section\)](#)
- [Section 4. Study Population Selection](#)

In addition, in order to emphasize the distinction between the key eligibility criteria in the Synopsis and the full list of criteria presented in Section 4, the following changes have been made in the Synopsis:

- “(not a complete list)” has been added to the Eligibility Criteria heading.
- The criteria are bulleted rather than numbered.
- The list of Key Exclusion Criteria has been shortened by removing the following criteria:
 6. Subject is taking valpromide, progabide, valproic acid, or other known inhibitors of epoxide hydrolase, or subject is taking azathioprine or mercaptopurine.
 7. Subject is receiving chronic treatment with more than 325 mg of salicylates per day.
 9. Subject is taking any other drug approved for use as a urate-lowering medication other than allopurinol or febuxostat (eg, pegloticase, probenecid, benzbromarone) within 4 weeks prior to Screening or during Screening.
 10. Subject previously participated in a clinical study involving lesinurad (RDEA594) or verinurad (RDEA3170) and received active treatment or placebo, or has taken commercially-available lesinurad.

Finally, the following have been added under [Key Exclusion Criteria](#) in the Synopsis:

- Subject has a history of glomerulonephritis.
- Subject is pregnant or breastfeeding.

2.3. Pregnancy and Fertility Testing

A follicle-stimulating hormone test (FSH) test has been added. The FSH test will be done at Screening Visit 2 (SV2) only, and only for females with 12 months of spontaneous amenorrhea who are not surgically sterile. The human chorionic gonadotropin (HCG) test will be done at SV2 for all females and again at Month 12 for all females except those who are surgically sterile or not of childbearing potential as confirmed by the SV2 FSH.

Text regarding pregnancy and fertility tests is included in the following sections of the protocol:

- [6.9.1. Clinical Safety Laboratory Assessment](#)
- [8.1.2. Screening Visit 2 \(3 Weeks After Screening Visit 2 \[\$\pm\$ 3 Days\]\)](#)
- [Appendix A. Schedule of Events.](#)

2.4. Medical History

[Section 6.2. Medical History](#) was revised to clarify that a complete medical history will not be collected until the Baseline Visit; only medical history data needed to determine subject eligibility for the study will be collected during Screening.

Text in the following sections was revised accordingly:

- [8.1.1. Screening Visit 1 \(Approximately 28 Days Before Day 1\)](#)
- [Appendix A. Schedule of Events.](#)

2.5. Rescreening of Subjects

Section 8.1.4. Option for Rescreening was renumbered and renamed [Section 8.2 Rescreening of Subjects](#). Text specifying that a subject being rescreened should receive a new screening number was added.

2.6. Study Medications

2.6.1. Sourcing and Dispensing of Study Medications

Text has been added to [Section 5.2. Other Study Treatments](#) to specify that commercially available allopurinol, febuxostat, and colchicine drug product will be used, and that the relevant product labeling will be provided to Investigators.

[Section 5.8.1. Site Receipt](#) was revised to clarify that it is specific to IP.

[Section 5.8.4. Compliance and Accountability](#) was revised to specify that except at the Month 1 Visit, IP will not be redispensed.

2.6.2. XOI Use Prior to Randomization

Text in the following sections has been revised to consistently specify that subjects should be on a stable, medically appropriate dose of XOI for at least 4 weeks prior to Screening and throughout the Screening Period:

- [Synopsis \(Methodology section\)](#)

- [Synopsis \(Eligibility Criteria section\)](#)
- [1.3. Rationale for Study Design and Dose Selection](#)
- [3.1. Overall Study Design and Plan.](#)

2.6.3. XOI Use After Permanent Discontinuation of IP

Text in the following sections of the protocol was amended to reflect that subjects who discontinued IP have the option to continue on study-supplied XOI until their End of Study Visit:

- [Section 3.1. Overall Study Design and Plan](#)
- [Section 5.3.2.1.2. Other Reasons, and Procedures, for Permanent Discontinuation of Investigational Product.](#)
- [Section 8.4. Follow-Up Period.](#)
- [Appendix A. Schedule of Events.](#)

2.6.4. Interruption and Discontinuation of Study Medications

[Section 5.3 Selection and Timing of Dose for Each Subject](#) was reorganized as follows to clarify in which subsection the Investigator can find instructions on each topic:

5.3.1. General Instructions for Dosing

5.3.2. Dose Adjustments, Interruptions, and Discontinuations

5.3.2.1. Investigational Product and Xanthine Oxidase Inhibitors

5.3.2.1.1. Interruption or Discontinuation of Investigational Product due to Changes in Kidney Function

5.3.2.1.2. Other Reasons, and Procedures, for Permanent Discontinuation of Investigational Product

5.3.2.2. Gout Flare Prophylaxis

5.3.2.2.1. Colchicine

5.3.2.2.2. Low-Dose Corticosteroids

In addition, text was added to [Section 5.3.2.1.2.](#) to stress the importance of subject retention in the study after discontinuation of IP.

2.6.5. Gout Flare Prophylaxis

The protocol now more clearly states that gout flare prophylaxis is required, and the rationale for this requirement has been added to the Synopsis.

The following sections of the protocol are affected:

- [Synopsis \(Methodology section\)](#)
- [1.3. Rationale for Study Design and Dose Selection](#)
- [3.1. Overall Study Design and Plan](#)

- [Colchicine](#).

2.7. Premature Discontinuation From the Study

[Section 6.16](#). Early Study Withdrawal has been renamed “Premature Discontinuation from the Study” to clarify that the text covers all reasons for subject failure to complete the study, whether subject-initiated or not. “Investigator decision” has been added as a potential reason for premature discontinuation. In addition, language encouraging Investigators to maximize subject retention and minimize missing data has been added.

2.8. Analysis Populations

The following text has been added to [Section 9.3. Analysis Populations](#): “The Per-Protocol Population will be defined as all subjects in the Intent-to-Treat (ITT) population without major protocol deviations, defined prior to unblinding of the study. Select analyses (to be specified in the Statistical Analysis Plan [SAP]), will be repeated on the PP population.”

2.9. Definition of Adverse Events

The language in [Section 6.11.1. Adverse Event Definition](#) was revised to remove redundant text, clarify that any clinically relevant deterioration in clinical laboratory values or vital signs should be reported as an AE, and to specify that protocol-mandated permanent discontinuation of IP per the sCr/eCrCl criteria described should be reported as an AE.

